3.4 Other analyses (secondary endpoints in pivotal study)

This endpoint is defined as:

- Proportion of patients with positive-margins after standard of care breast-conserving surgery who have a LUM Imaging System signal in the cavity above the threshold as defined by the tumor detection algorithm (i.e., a positive LUM signal). The endpoint is estimated as:

$$\frac{\# \text{ positive margin patients after SOC with LUM signal above the threshold}}{\# \text{ positive margin patients after SOC}}$$

- Proportion of subjects with pathology-positive margins after standard of care breast-conserving surgery, for whom additional therapeutic shaves resulted in pathology-negative margins. Note: This efficacy metric also estimates the potential reduction in re-excision surgeries following standard of care breast-conserving surgery that resulted from a positive SOC margin. This is estimated as:

$$\frac{\# \text{ positive margin patients after SOC with all final negative margins after the LUM procedure}}{\# \text{ positive margin patients after SOC}}$$

- Mean absolute volume (cc) of tissue removed from therapeutic shaves. For each subject, absolute shave volume will be calculated as length (c) \times width (c) \times depth (c) for each therapeutic shave with the sum by subject of all therapeutic shaves. Dimensions for the tissue will be obtained as entered in the case report form from the standard of care pathology report. Subjects with no therapeutic shaves taken will have a therapeutic shave volume of 0cc. The proportion of the subjects with and without therapeutic shaves will be reported. The mean and median (with 90% confidence interval) of the total surgery volume of tissue excised and total volume of the SOC tissue will be reported grouped by the subjects with or without therapeutic shaves.

LUMICELL CONFIDENTIAL

This document is confidential. Do not disclose or use except as authorized.

- c. Mean contribution of therapeutic shave volume to total volume of tissue removed. The ratio of therapeutic shave volume to total volume of resection (main specimen + SOC shave volume + therapeutic shave volume) tissue removed will be calculated in the total population and in the population with therapeutic shaves removed. For each subject, the volume for each piece of tissue will be calculated as length (c) × width (c) × depth (c), and the dimensions will be obtained as entered in the case report form from the standard of care pathology report. The mean and median (with 90% confidence interval) will be reported.
- d. Average number of SOC shaves and therapeutic shaves taken per subject overall and by type of SOC lumpectomy procedure (i.e., lumpectomy with comprehensive shaves vs. lumpectomy with or without selective shaves).
- e. Number of second surgeries recommended as a result of final positive margins.
- f. Rate of second surgery procedures as a result of final positive margins.
- g. Rate of second surgery procedures as a result of final positive margins.
- h. Rate of cancer found in second surgeries.
- i. Number of second surgeries for each subject.
- j. Number of images per subject from the cavity after SOC and first round of the therapeutic shaves.
- k. Number of LUM images having LUM-positive signal and therapeutic shaves taken.
- l. Fluorescence intensity mean of the cavity images, LUM positive images and positive images with shave after SOC and after one round of the therapeutic shaves.
- m. Number of device issues and malfunctions and their impact to data capture.

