4.8.3 Missing and spurious data

During Luminicell-guided imaging, when there is not enough tissue to be removed (e.g. too close to skin or too close to the chest wall) no LUM image shall be recorded because it does not generate an actionable result.

In the case where the LUM Imaging System indicates that a therapeutic shave needs to be removed but the surgeon decides not to follow this guidance, the reason for not doing so will be recorded in the patient's CRF or during imaging. These instances are considered as a protocol deviation. There are other cases when the shavings reach protocol limits so no shaving will be performed. In these cases, the data will be included in the performance evaluation as is - that is no Luminicell-guided shave-taken will be considered as no removing of cancer or positive margin. However, they will be considered as a detection if there are cancer in the re-excision or if there are positive margins on the corresponding orientations.

Occasionally, a cavity image may be recorded from an unintended region or the image may be deemed as low quality (blurry, out of focus, etc.). For example, the surgeon realizes that he/she placed the device in the wrong location within the cavity after recording an image. Since the LUM software does not allow to overwrite saved images, this situation will be documented, the image will be labeled as "image retaken", "eval", "initialscan" or "transient" and the image will be excluded from the analysis. In addition, images labeled as "lens issue" will be considered as a device malfunction and will be excluded from the analysis.

Other cases are handled as follows:

- When a patient was prescribed Letrozole adjuvant therapy prior to surgery, the patient will be removed from the device performance evaluation.
- When the time from injection of LUM015 to lumpectomy incision is greater than 6 hours due to unplanned surgical delays, the patients will be removed from the device performance evaluation.
- For the re-excision rate endpoints, all patients undergoing a re-excision will be included in the analysis.
- When an image is indicated negative by LUM Imaging System but the shave is taken due to X-ray or pathology suggestion, it will be kept for sensitivity and specificity evaluation, however, for the analysis related to margins, it is conditional and described in g.

LUMICELL CONFIDENTIAL

This document is confidential. Do not disclose or use except as authorized.

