- l. For reported microinvasive cancer, adjudicated correction will be provided external to the eCRF and will be used to change the margin type from Invasive to DCIS following NCCN guidelines.
- m. Margins for SOC and final margins will be derived from the tumor distance to margins. If there is a discrepancy between the derived margins based on distance and the margin status determined by the clinical site (could be due to different criteria used by the clinical sites), adjudication of the margin status will be done by Luminicell based protocol defined margin criteria (section 3.1).

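### SAP 4.8.3 brings patients into the re-excision rate because they were re-excised, and SAP 3.4 items f and g are the same endpoint with no stated denominator

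*SAP*

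**What the plan says.** SAP 3.4 has five items on second surgery.

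- Item e is a count: "Number of second surgeries recommended as a result of final positive margins".
- Items f and g are word for word the same: "Rate of second surgery procedures as a result of final positive margins". Neither names a denominator, and neither says whether the unit is patients or operations.
- Item h is "Rate of cancer found in second surgeries", and item i is "Number of second surgeries for each subject". Neither is restricted by the reason for surgery.

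SAP 4.8.3 lists handling rules for other cases. The first reads: "When a patient was prescribed Letrozole adjuvant therapy prior to surgery, the patient will be removed from the device performance evaluation". The second applies the same removal "When the time from injection of LUM015 to lumpectomy incision is greater than 6 hours due to unplanned surgical delays". The third follows directly: "For the re-excision rate endpoints, all patients undergoing a re-excision will be included in the analysis". No endpoint in 3.4 carries the name re-excision rate, so items f and g are the natural referent, but the SAP does not say so.

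SAP section 2 makes the mITT population, meaning all imaged patients, primary for the efficacy metrics in section 3. SAP 4.4 analyses secondary proportions with binomial methods. Protocol 8.5 follows each subject until no further surgery is needed, and its example of a second surgery covers both mastectomy and lumpectomy re-excision.

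**The concern.** A rate needs a population fixed without regard to the outcome. The third rule in 4.8.3 names only patients who had the outcome. Coming straight after two removals, it reads as an exception that lets re-excised patients back in and leaves the others out. Inclusion then depends on the event being counted.

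A second difficulty is the numerator. Items f and g count operations done because of final positive margins, whereas the 4.8.3 rule mentions no reason. Two analysts working from the same SAP could report different rates. The repetition of f as g adds to the doubt: either one item is redundant, or an intended endpoint was lost.

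Protocol 3.2 puts forward fewer re-excisions as a possible benefit of the system, and SAP 3.4 labels its analyses as secondary endpoints of the pivotal study. A reader of the Phase C results will therefore look at this rate, and it should have one meaning.

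**Working it through.** The plan states no second-surgery rate, so there is no figure to reproduce. All inputs below are assumptions for illustration, except the ceiling of 250 patients (protocol 15.2).

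**1. Direction of the effect**

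Let x of n retained patients be re-operated. Among the removed patients, let k be re-operated and m not.

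- Everyone kept: (x + k)/(n + k + m)
- All removed patients left out: x/n
- Literal 4.8.3 rule: (x + k)/(n + k)

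The literal rule exceeds the first whenever m > 0 and at least one patient is re-operated. It exceeds the second whenever k > 0 and x < n. The direction is therefore upward against either coherent population, whatever the inputs.

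**2. Worked example**

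Assume 100 imaged patients and 12 re-operated. Ten are removed under the first two rules, of whom 2 were re-operated. Then x = 10, n = 90, k = 2, m = 8.

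- Everyone kept: 12/100 = 12.0%
- All ten left out: 10/90 = 11.1%
- Literal rule: 12/(90 + 2) = 12/92 = 13.0%

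**3. Range**

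Let r be the true rate, the same in removed and retained patients, and e the share removed. The literal rule gives r / [(1 − e) + e·r].

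| r | e | Reported rate |
|---|---|---|
| 10% | 2% | 0.10/(0.98 + 0.002) = 10.2% |
| 10% | 10% | 0.10/(0.90 + 0.01) = 11.0% |
| 20% | 2% | 0.20/(0.98 + 0.004) = 20.3% |
| 20% | 10% | 0.20/(0.90 + 0.02) = 21.7% |

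The excess is about 0.2 to 1.7 percentage points. It is zero if nobody is removed.

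**4. Numerator**

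Let s be the share of second surgeries done for reasons other than positive margins. The margin-driven rate is r(1 − s). With s from 10% to 30%:

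- r = 10% becomes 9.0% down to 7.0%
- r = 20% becomes 18.0% down to 14.0%

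The choice of numerator therefore moves the rate by 1 to 6 points. With the maximum of 250 patients and r = 20%, that is 50 patients for any reason against 45 to 35 for margins. The gap is zero if every second surgery is for positive margins.

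**The case against.** The strongest reply is that the third rule in 4.8.3 only defines a population. It follows two removals from the device performance evaluation and may mean no more than that those removals should not shrink the re-excision analysis. Items f and g would still set the numerator, and SAP section 2 already supplies mITT as the default denominator. This is plausible. It means the numerator question is an ambiguity and not a proven contradiction. It does not rescue the wording, because even as a population rule it names only re-excised patients and is silent on removed patients who were not.

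A reader might infer more than the documents support:

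- **That the SAP gives no rate for second surgery of any cause.** Item i counts second surgeries per subject with no restriction on reason, so such a rate can be derived. What is missing is a specified output.
- **That sponsor adjudication of margin status (4.8.3 item m) lowers the rate.** Item m settles whether a margin is positive when the derived and site calls differ. It does not reclassify why a patient was re-operated, and the phrase in f and g can equally mean the site's actual reason. Adjudication can also move status either way. What stands is that f does not say whose call governs.
- **That the worked example should read 12/90 = 13.3%.** The rule includes the returning patients in the analysis, so they belong in the denominator as well.
- **That protocol 8.5 requires the reason for a second surgery to be recorded.** It requires follow-up and cites positive margins only as an example.

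It is also fair to say that SAP section 1 states that the protocol pre-defined no hypothesis-tested endpoints.

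**Conclusion.** The point holds in limited form. Followed as written, the 4.8.3 rule conditions inclusion on the outcome and biases the second-surgery rate upward. Separately, f and g duplicate each other, have no stated denominator, and may or may not be overridden by 4.8.3 as to reason.

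In the worked example the bias is 13.0% against 12.0%. Across removed shares of 2% to 10% and true rates of 10% to 20%, it is 0.2 to 1.7 points. These sizes rest wholly on assumed inputs. The direction rests only on the literal reading of the rule and on the removals applying to these endpoints, which the SAP does not settle.

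Severity is modest. The analyses are descriptive, the study has a single arm, and the protocol's main aims are to refine the algorithm and train surgeons.

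**What to change.** 1. Reword the third rule in SAP 4.8.3 along these lines: *For the second-surgery rate endpoints, all mITT patients are included, whether or not they had a second surgery; the Letrozole and >6-hour removals do not apply.*
2. Keep item f as the margin-driven rate, with mITT patients as denominator and the patient as unit. State whose margin determination decides that a second surgery was margin-driven.
3. Replace the duplicate item g with the proportion of mITT patients having any second breast surgery, re-excision or mastectomy. This can be derived from item i.
4. Leave e and i as counts, and keep second surgeries as the denominator of h. An mITT denominator would turn h into a different quantity.
5. List patients re-operated for a margin the site called positive but whose adjudicated margin is negative, so that a reader can see how far the choice in step 2 matters.

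The cost is SAP wording and one listing. Step 3 needs only follow-up that protocol 8.5 already requires. Steps 2 and 5 need the reason for each second surgery. Items e to g already presuppose it, but protocol 8.5 does not require it, so the case report form should be checked. The population change would tend to lower the reported rate relative to the literal rule. The added any-reason rate cannot be lower than the margin-driven one.

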3.5 Safety measurements analysis

The safety measurements include the following:

- a. Adverse events stratified by severity and relatedness to drug/device
- b. Serious adverse events stratified by severity and relatedness to drug/device
- c. Adverse events by preferred term (sorted by descending occurrences for each preferred term)
- d. Summary of adverse events, overall and split by expectedness to drug/device
- e. Comparison of adverse events in subjects that have at least one therapeutic shave versus subjects that have no therapeutic shaves

3.6 Exploratory measurements

- Collect exploratory data on tissue types found in therapeutic shaves

4 Statistical Methods

4.1 Demographic and baseline characteristics

Demographic and baseline characteristic summaries will be provided. These measures include; age, race and ethnicity, menopausal status, mammographic breast density, palpability, cancer histologic type, tumor size, node positive patients, and tumor receptor status (ER/PR/HER2), and baseline body mass index (BMI) calculated from weight and height. Statistics for continuous variables will include mean, median, standard deviation (SD), minimum, maximum and sample

LUMICELL CONFIDENTIAL

This document is confidential. Do not disclose or use except as authorized.

size for the overall sample and for subgroups. Binary variables will be described with frequencies and percentages for the overall sample and subgroups. Demographic and baseline characteristics will be summarized by overall descriptive statistics for analysis populations

4.2 Residual cancer removal

This proportion will be evaluated using Binomial distribution method to report the point value and the two-sided 95% confidence interval.

4.3 Diagnostic performance (sensitivity, specificity and Youden Index)

Sensitivity and specificity will be reported based on the 2x2 contingency table (Table 1) including the point value as well as the two-sided 95% confidence interval.

Youden Index will be evaluated using the relationship:

$$\text{Youden Index} = \text{sensitivity} + \text{specificity} - 1 = \text{sensitivity} - \text{false positive rate}$$

where

$$\text{false positive rate} = 1 - \text{sensitivity} = \frac{\text{False Positives}}{\text{True Negatives} + \text{False Positives}}$$

A difference of proportions approach will be used to report the Youden Index point value and the two-sided 95% confidence interval.

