Although no pre-defined, hypothesis tested endpoints were included in the protocol, we will perform data analyses based on the proposed endpoint of the pivotal study protocol CL0007r07.

2 Analysis Populations

- Safety (SAF) population: the safety population includes all subjects who received study drug.
- Modified Intention To Treat (mITT) population: includes all SAF subjects excluding subjects who are not able to be imaged with the LUM Imaging System. That is, the mITT population includes all patients imaged with the LUM Imaging System and will be used as the primary analysis population for the efficacy metrics outlined in section 3.
- Per-Protocol Population: Includes mITT subjects who complete all study evaluations and are without any major protocol deviations. This per protocol population will be used to evaluate the efficacy metrics outlined in section 3.

3 Efficacy metrics analysis

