3.3.2 Definition of truth standard for diagnostic performance

The instrument diagnostic accuracy is measured by sensitivity and specificity on a per-tissue basis. Because a LUM-guided shave does not exist when a negative LUM image is indicated we propose a hierarchical approach to determine the truth standard as depicted in Figure 2. The highest truth standard is whether pathology finds cancer in a tissue shave removed from the area that was imaged in the cavity. When a shave does not exist, then whether tumor is found in a re-excision surgery is considered as the truth standard. When neither a shave nor a second surgery exists for a given orientation that was imaged, the margin assessment of that orientation is used as truth standard. We believe that the hierarchical approach outlined to determine the truth standard is the most meaningful and practical assessment of device accuracy to predict the presence of cancer in the cavity.

LUMICELL CONFIDENTIAL

This document is confidential. Do not disclose or use except as authorized.

True positive = truth standard positive & Lum cavity image positive

False negative = truth standard positive & Lum cavity image negative

True negative = truth standard negative & Lum cavity image negative

False positive = truth standard negative & Lum cavity image positive

Figure 2: Definition of truth standard to evaluate the LUM Imaging System diagnostic performance.

When a therapeutic shave and re-excision are not available for an orientation, the margin from the prior resected tissue of the corresponding orientation will be used as ground inferred truth for evaluation (Figure 3).

The orientation of the tissue removed during a re-excision is typically noted in the pathology report and matches the orientation in which a positive margin was identified from the initial surgery. However, there will be instances in which the orientation of the tissue removed during a re-excision is not specified. In cases of unclear orientation of the tissue removed during re-excisions, it will be assumed that the re-excision was intended to address only the orientations with positive margins and pathology findings from the re-excision (tumor found/not found) will be applied to those orientations.

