4.8.2 Multiple images to cover entire shave or multiple shaves for one image

To accurately evaluate the study endpoints, it is critical that images are collected from the entire lumpectomy cavity surface. To achieve this, multiple images may be required to record the LUM assessment for an entire orientation (e.g. 2 images to cover the entire superior orientation) but a single shave may exist. When multiple images exist for a given orientation or shave, the combination of the images will be considered as one single output as described below:

- All images for a given orientation or shaved region are LUM negative, then the LUM result for the entire orientation or shaved region is considered as LUM negative.

LUMICELL CONFIDENTIAL

This document is confidential. Do not disclose or use except as authorized.

- If one or more of the images for a given orientation or shaved region is LUM positive, then the LUM result for the entire orientation or shaved region is considered as LUM positive.

When there are more than one shave for a single image, the pathology finding for the combination of the shaves will be considered as one as follows:

- If no tumor is found on the shaves, then the combination of the shaves is considered as truth standard negative.
- If any of the shaves has tumor, then the combination of the shaves is considered as truth standard positive.

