4.8.4 Not enough tissue left for imaging or removing a therapeutic shave

LUMICELL CONFIDENTIAL

This document is confidential. Do not disclose or use except as authorized.

This is a list of certain orientations in a given subject in which there is not enough tissue left for further imaging or removing a therapeutic shave. The margins of these orientations in the list will be ignored and will be treated as negative margin from the efficacy analyses.

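### SAP 4.3 sets the per-tissue specificity interval from a pooled 2x2 table with no allowance for several orientations per patient, so it is too narrow if calls within a patient are correlated

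*SAP*

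**What the plan says.** SAP 3.3.2 sets the unit of analysis: "The instrument diagnostic accuracy is measured by sensitivity and specificity on a per-tissue basis". Protocol 5.3 describes typically 6 oriented surfaces per lumpectomy, and Protocol 15.2 accepts that one patient may give more than one pathology positive.

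SAP 4.3 then says "Sensitivity and specificity will be reported based on the 2x2 contingency table (Table 1) including the point value", together with a two-sided 95% confidence interval. For the Youden Index, "A difference of proportions approach will be used to report the Youden Index point value and the two-sided 95% confidence interval". SAP 4.3 names no interval formula or variance estimator. The neighbouring SAP 4.2 and 4.4 use binomial methods for other proportions.

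The only pooling rule is in SAP 4.8.2: "When multiple images exist for a given orientation or shave, the combination of the images will be considered as one single output". It works within an orientation or shave, not across the orientations of one patient. Neither document mentions clustering, robust variance, GEE or patient-level resampling for these estimates.

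Not every orientation contributes. SAP 4.8.3 says that where too little tissue remains, "no LUM image shall be recorded because it does not generate an actionable result", and SAP 4.8.4 keeps a list of orientations where "there is not enough tissue left for further imaging or removing a therapeutic shave".

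**The concern.** A pooled 2x2 table with an ordinary binomial interval treats every orientation as an independent observation. Several shared features could make the calls on truth-negative orientations of one patient alike:

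- one detection threshold, set from that patient's own cavity images (Protocol 4.5);
- one interval from injection to surgery, anywhere from 2 to 6 hours (Protocol 9.8);
- one device size, chosen for that surgery (Protocol 4.4);
- one background signal, since cathepsins are not confined to cancer cells (Protocol 4.3).

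A poorly set threshold, for example, would move all calls in that patient in the same direction. With positive correlation the data carry less information than the count of orientations suggests, and the interval is too narrow.

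At stake is the reported precision of a metric that the SAP labels a pivotal co-primary. Protocol 15.5 also uses Phase B and Phase C data to estimate expected pivotal results, although no rule there uses this interval.

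**Working it through.** **The plan's own figures.** Protocol 15.2 cites 19 pathology positives from 40 Phase B patients and asks for 32 more. Expected patients: 32 / (19/40) = 67.4, against about 67 stated. The margin of error of about 7% for sensitivity at 19 + 32 = 51 positives also reproduces: the exact lower limit for 51/51 is 0.025^(1/51) = 0.930, a margin of 7.0%. The Wald form gives 7.0% at a sensitivity of 0.93. Both forms treat the 51 samples as independent. The documents give no matching figure for specificity.

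**Assumptions not in the documents.** Specificity 85%; ICC 0 to 0.3; 3 to 6 imaged orientations per patient.

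**Formulae.** With k imaged orientations and 67 patients, truth-negatives per patient are m = (67k − 32)/67. The design effect is DE = 1 + (m − 1) × ICC. The half-width is 1.96 × √(p(1 − p)/n) × √DE.

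**Six orientations.** n = 67 × 6 − 32 = 370 and m = 5.52. The pooled half-width is 1.96 × √(0.85 × 0.15/370) = 3.6 points. Coverage is from simulation with a shared patient effect on the probit scale, 10,000 runs.

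| ICC | DE | √DE | Half-width needed (points) | Coverage, unclustered exact CI | Coverage, clustered Wilson CI |
|---|---|---|---|---|---|
| 0 | 1.00 | 1.00 | 3.6 | 96.2% | 95.5% |
| 0.02 | 1.09 | 1.04 | 3.8 | 95.0% | 95.0% |
| 0.05 | 1.23 | 1.11 | 4.0 | 93.5% | 94.6% |
| 0.1 | 1.45 | 1.21 | 4.4 | 90.5% | 94.5% |
| 0.2 | 1.90 | 1.38 | 5.0 | 85.5% | 94.2% |
| 0.3 | 2.36 | 1.54 | 5.6 | 80.8% | 94.6% |

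A beta-binomial model gives nearly the same exact-interval coverage at ICC 0.1, 0.2 and 0.3: 91.2%, 85.6% and 81.3%. Specificity of 65% or 95% changes coverage by no more than 1 point.

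**Fewer imaged orientations, ICC 0.1 to 0.3.**

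| k | m | √DE | Coverage, unclustered exact CI |
|---|---|---|---|
| 5 | 4.52 | 1.16–1.43 | 91–83% |
| 4 | 3.52 | 1.12–1.33 | 92–87% |
| 3 | 2.52 | 1.07–1.21 | 94–91% |

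**At the 250-patient cap, 6 orientations.** Positives: 250 × 0.475 = about 119, leaving 1,381 truth-negatives. The half-width of 1.9 points should be 2.3 to 2.9, and coverage is still 90–80%. More patients do not cure the fault, because the factor depends only on m and the ICC.

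**Sensitivity.** Positives average 19/40 = 0.475 per patient, so clustering matters little: an unclustered exact interval covers 96–98%.

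**Youden Index.** Coverage at ICC 0.1–0.3, with 32 positives placed at random:

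| Interval | Sensitivity 85% | Sensitivity 93% | Sensitivity 97% |
|---|---|---|---|
| Plain Wald | 90.8–91.4% | 87.3–88.4% | 82.9–84.4% |
| Percentile patient bootstrap | 92.6–93.9% | 89.5–91.4% | 87.8–90.7% |
| Newcombe, unclustered | 94.2–94.9% | 93.2–95.2% | 90.7–93.3% |
| Newcombe, clustered | 96.1–96.5% | 96.3% | 95.1–96.0% |

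If positives come in pairs within patients, unclustered Newcombe covers 90.1–94.5% and clustered 95.2–96.1%. Clustering adds 0.6 to 1.4 points of half-width, or up to 2.5 with pairs.

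The bootstrap fails when there are no false negatives, which happens in 38–39% of runs at 97% sensitivity and is what Protocol 3.2 reports for Phase B. With 32/32 detected and specificity 85%, Newcombe gives 73.6 to 88.3 unclustered and 72.9 to 89.3 at DE 1.90. A bootstrap would keep only about ±5.0 points, all from specificity.

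**The case against.** The strongest reply is that everything turns on an ICC the documents do not give. Protocol 8.2 has the surgeon image the tumor bed to set a normal-tissue baseline for the threshold. That step is aimed at patient-level differences in background, where the injection interval would also act. Protocol 4.4 states that the two device sizes are optically equivalent, though on excised tissue. What is left is mainly error in the threshold itself, of unknown size. The ICC could be 0.02 to 0.05, where coverage is 95.0–93.5%. Six is also the number of surfaces typically defined, not the number imaged. This stands as a limit on the size of the effect. It does not show that the ICC is zero, and an interval that is valid either way is available at almost no cost.

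Second, SAP 4.3 names no method, so a clustered interval is not ruled out. True, but a 2x2 table beside binomial wording leads naturally to an independent-units interval, and leaving the method open does not prevent that.

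Third, nothing is decided on this interval. The SAP itself says "Although no pre-defined, hypothesis tested endpoints were included in the protocol", and the algorithm lock in Protocol 15.2 depends on sensitivity. Subject-level listings (SAP 4.8) would also allow later recalculation. All of this is correct and limits the consequence to reported precision.

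Finally, the Newcombe form combines the two proportions as if independent, although they come from the same patients. In the simulations it slightly over-covers, which is the safer direction.

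**Conclusion.** The concern holds. Following SAP 4.3 as written gives a specificity interval that is too narrow whenever calls within a patient are positively correlated, and nothing elsewhere in the plan corrects this. The correlation is plausible from the protocol but not established by it. At an assumed ICC of 0.1 to 0.3 the effect is clear with 4 to 6 imaged orientations and modest with 3; at 0.05 or below it is small. The Youden Index interval inherits the gap. Point estimates do not change, the sensitivity interval changes little, and no type I error is involved. The point should be fixed because the SAP promises a 95% interval for a metric it labels a pivotal co-primary. Confidence in the size is medium, because the ICC, the specificity and the number of imaged orientations are all assumed.

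**What to change.** In SAP 4.3, keep the 2x2 point estimates and specify the intervals:

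1. **Specificity.** Treat the patient as the cluster. One suitable choice is Wilson limits with effective sample size n / DE, where DE is the cluster-robust variance divided by the binomial variance, floored at 1. A patient-level bootstrap is also acceptable for specificity (coverage 93–94% at ICC 0.1–0.3). Report the estimated ICC.
2. **Sensitivity.** Use an exact interval, or Wilson limits with a clustered effective sample size where this can be estimated.
3. **Youden Index.** Keep the difference-of-proportions approach, but specify a Newcombe interval built from Wilson limits with the clustered effective sample sizes. Use DE = 1 for sensitivity if there are no false negatives. Do not use a percentile bootstrap here.

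Separately, as an editorial correction that adds no weight to the point, SAP 4.3 equates the false positive rate with one minus sensitivity. It should read one minus specificity, as the fraction printed beside it shows.

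The cost is a few sentences and a few lines of code. If the ICC is 0, the specificity half-width grows by about 0.1 point (3.63 to 3.74).
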